Treatment

Treatment A: days 1–4, administration of placebo with 240 mL of water
day 5, administration of placebo + 40 mg gliclazide with 240 mL of water

Treatment B: days 1–4, administration of 20 mg omeprazole with 240 mL of water
day 5, administration of 20 mg omeprazole + 40 mg gliclazide with 240 mL of water

*Wash-out period of at least 7 days

Blood collection

Venous blood samples will be collected on day 5 and day 19 for gliclazide, glucose and insulin quantification, through an indwelling intravenous cannula in the arm or by direct venepuncture (in the case of cannula blockage).

A total of 17 blood samples, 5 ml each, will be taken, thus the total blood volume of 85 ml will be taken during 24 hours, which is over 5 times less than the standard 450 ml drawn during voluntary blood donation.

Blood sampling for gliclazide quantification

- gliclazide: pre-dose (0 h), 0.5, 1, 1.5, 2, 2.5, 3, 3.5, 4, 4.5, 5, 6, 7, 8, 10, 12, and 24 h

Blood sampling for glucose and insulin quantification

- glucose: pre-dose (0 h), 0.5, 1, 1.5, 2, 2.5, 3, 3.5, 4, 4.5, 5, 6, 7, 8, 10 and 12 h
- insulin: pre-dose (0 h), 0.5, 1, 1.5, 2, 2.5, 3, 3.5, 4, 4.5, 5, 6, 7, 8, 10 and 12 h

Blood glucose levels will be measured immediately after sampling. Serum samples for insulin and gliclazide quantification will be obtained and stored in properly labelled tubes at -80°C until the analysis.

Gliclazide concentration analysis

Serum gliclazide concentration will be analysed at the Biomarker and Drug Analysis Core Facility, School of Medicine, University of Dundee, by using a stable isotope dilution LC-MS method.

Glucose and insulin quantification

Glucose concentrations will be measured at the laboratory of the General Hospital.

Insulin concentrations will be quantified by enzyme-linked immunosorbent assay (ELISA) using commercially available kit.

Pharmacokinetic analysis

- C_{max} : Gliclazide maximum concentration
- t_{max} : Time to reach C_{max}
- AUC_{0-t} : Area under the concentration–time curve (AUC) up to the last concentration measured
- $\text{AUC}_{0-\infty}$: Area under the concentration–time curve (AUC) extrapolated to infinity
- $t_{1/2}$: Elimination half-life
- $C_{\text{L}/\text{F}}$: Apparent oral clearance
- $V_{\text{d}/\text{F}}$: Apparent volume of distribution

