PK parameters will be calculated by a noncompartmental analysis using PKSolver a program for PK and PD data analysis in Microsoft Excel. Gliclazide maximum concentration (C_{max}) and time to reach C_{max} (t_{max}) will be determined by the inspection of the concentration–time data. The area under the plasma gliclazide concentration–time curve (AUC) up to the last concentration measured (AUC_{0-t}) will be determined using the linear trapezoidal rule. The AUC will be extrapolated to infinity ($\text{AUC}_{t-\infty}$) using C_t/k_{el} , where C_t is the last measured gliclazide concentration and k_{el} is the elimination rate constant that will be estimated from the slope of the best-fit line determined by linear regression analysis of the log-transformed concentration-time curve. The elimination half-life ($t_{1/2}$) will be calculated using the following equation: $t_{1/2}=\ln(2)/k_{\text{el}}$. The apparent oral clearance (CL/F) will be calculated as $\text{dose}/\text{AUC}_{0-\infty}$. The apparent volume of distribution ($V_{\text{d}/\text{F}}$) will be calculated as $\text{dose}/\text{AUC} \times k_{\text{el}}$.

Pharmacodynamic parameters

- C_{\min} : Glucose minimum concentration
- $C_{\text{avg } 0-4}$: Average glucose concentration in the period 0–4 h
- $C_{\text{avg } 0-12}$: Average glucose concentration in the period 0–12 h
- AUC_{0-4} : Area under the glucose concentration–time curve from 0 to 4 h
- AUC_{0-12} : Area under the glucose concentration–time curve from 0 to 12 h

- C_{\min} : Insulin minimum concentration
- $C_{\text{avg } 0-4}$: Average insulin concentration in the period 0–4 h
- $C_{\text{avg } 0-12}$: Average insulin concentration in the period 0–12 h
- AUC_{0-4} : Area under the insulin concentration–time curve from 0 to 4 h
- AUC_{0-12} : Area under the insulin concentration–time curve from 0 to 12 h

To compare the PD effects of gliclazide, the areas under the glucose and insulin concentration–time curve from 0 to 4, and 0 to 12 h after the administration of gliclazide will be calculated using the linear trapezoidal rule. The minimum glucose and insulin concentration will be determined by observation of the concentration–time data, and mean concentrations from 0 to 4 h and from 0 to 12 h will be calculated by dividing the area under the glucose/insulin concentration–time curve by the corresponding time interval.

Safety assessment and precaution measures

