The volunteers will undergo a detailed physical, ECG, and laboratory examination upon inclusion in the drug interaction study. The subjects will be contacted within 14 days of study completion in order to confirm the adequate post-study status.

If any clinical reasons arise that could endanger health status of the subjects by taking blood samples, the blood samples will not be drawn. Considering that bruising, bleeding, infection or pain may occur at the site of venepuncture and cannulation, these procedures will be performed by experienced medical staff to minimise the risk of excessive bleeding or bruising, and a topical anaesthetic may be used, if required, to reduce the pain.

Since this combination of drugs can potentially induce risk of hypoglycaemia, administration of the two drugs will be carried out in the hospital where the subjects will be hospitalised for 24 h and will be continuously under direct medical supervision. In order to avoid the risk of hypoglycaemia, subjects will receive 8 meals (breakfast, lunch, dinner and 5 snacks). In case of any symptom suggestive of hypoglycaemia (nervousness, sweating, intense hunger, trembling, weakness, palpitations), the blood glucose level will be measured using a glucometer and one of the standard measures of raising blood sugar will be applied, such as administration of 20% oral glucose solution, glucose solution for intravenous use, or glucagon for intramuscular use.

In addition, systolic and diastolic blood pressure and heart rate will be measured in the supine position after a 5-minute rest, before drug intake and during the PK profiles at 2, 4, 12 and 24 hours after gliclazide administration.

Power analysis

For identification of clinically relevant drug-drug interaction, we will use the bioequivalence approach. The main outcome to be evaluated is the exposure to gliclazide, expressed as AUC_{0-t} . Sample size calculation was performed using SAS Proc Power procedure for equivalence test in 2x2 crossover design.²⁵ For an equivalence range of 80–125%, the within-subject coefficient of variation for the AUC values for gliclazide of 7.8% based on previous PK studies,^{26,27} and expected test/reference geometric

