mean ratios between 87–115%, 14 volunteers (7 individuals per sequence) are required to show the lack of interaction with 85% power. To account for potential drop-outs due to non-compliance or loss of follow up (assuming a drop-rate of 10%), a total of 16 subjects, CYP2C19 EM/UM metabolisers, will be randomised. To achieve this number, minimally 40 volunteers will be initially recruited.

Statistical analysis

The geometric mean will be calculated for each PK and PD parameter. Logarithmic transformation will be used for PK variables, except t_{max} , before the analysis. The ratios of the geometric means with 90% confidence intervals (CI) will be assessed by linear mixed models between the two treatment assignments: gliclazide and omeprazole coadministration to that of gliclazide and placebo. The statistical analyses will be performed using the SAS 9.3 software (SAS Institute Inc., Cary, NC).

Original scientific contribution and clinical significance of the research

This research will establish whether omeprazole can alter PK/PD of gliclazide, and thus increase the risk of serious hypoglycaemia with this recommended SU drug.

This study can unravel new, previously unrecognized drug-drug and drug-drug-gene interactions. If clinically relevant alterations in gliclazide PK/PD parameters are established, our findings can lead to changes in clinical practice with the aim of preventing serious, potentially life-threatening hypoglycaemia induced by gliclazide treatment.

Confidentiality and data protection

All clinical, laboratory and genetic data will be processed in a manner designed to protect the identity of the participants, in accordance with the rules of personal data protection and the guidelines of the Good Clinical Practice. Participants' privacy will be respected in all published and other public written data that will result from this study.

Withdrawal from the study

Participants are free to withdraw from the study at any time, without obligation to explain their decision.

Insurance

In accordance with the guidelines of Good Clinical Practice, the subjects will be insured under the terms of insurance for Clinical Trials.

Compensation of costs

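### The linear trapezoidal rule across the unsampled 12–24 h interval pulls the primary AUC0-t ratio toward 1 by about 1% if omeprazole slows gliclazide clearance, which modestly raises the error at the 1.25 limit

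*Combined protocol and SAP*

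**What the plan says.** The Power analysis section names the primary measure: "The main outcome to be evaluated is the exposure to gliclazide", expressed as AUC0-t. The Pharmacokinetic analysis section says that this area "will be determined using the linear trapezoidal rule". It gives no different rule for the declining part of the curve and no sensitivity analysis for the choice of rule. Under Blood sampling for gliclazide quantification, the later samples are at "4.5, 5, 6, 7, 8, 10, 12, and 24 h", so one trapezoid spans the second half of the 24 h window.

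The decision rule is equivalence: "For an equivalence range of 80–125" per cent in Power analysis, and in Statistical analysis "The ratios of the geometric means with 90% confidence intervals (CI) will be assessed by linear mixed models". The 90% interval implies two one-sided tests at 5% each.

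**The concern.** Drug concentrations after absorption fall roughly exponentially, and the plan treats them that way elsewhere: it takes the elimination constant from a regression of log concentrations and uses it for the tail beyond the last sample. Between 12 h and 24 h, however, it joins the two points with a straight line. That line lies above the curve, and the gap widens as elimination gets faster.

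The error would cancel in the ratio if both periods had the same elimination rate. Under the study hypothesis they do not: omeprazole inhibits the enzyme that clears gliclazide, so the placebo period is the faster one. Its AUC is inflated more and the ratio shrinks toward 1. This is a systematic shift in favour of declaring no interaction, in a study whose purpose is to find out whether the combination raises hypoglycaemia risk.

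**Working it through.** **Inputs from the documents.** Sampling times as listed; limits 0.80–1.25; 90% CI; "within-subject coefficient of variation for the AUC values for gliclazide of 7.8"%; "mean ratios between 87–115"%; 14 evaluable subjects, 16 randomised.

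**Assumptions not in the documents.** One-compartment oral model; half-life in the placebo period 4–20 h; absorption rate constant ka 0.4–1.2 per h; omeprazole changes clearance only; the last measurable concentration is at 24 h in both periods.

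**Step 1: the plan's own figure.** On the log scale, σ = √ln(1 + 0.078²) = 0.0779. SE = 0.0779 × √(2/14) = 0.0294, with 12 degrees of freedom. Exact power of the two one-sided tests is 85.1% at a ratio of 0.87 and 84.7% at 1.15, which agrees with the stated 85%. For dropout, 14/0.9 = 15.6, rounded up to 16. At a true ratio of 1.25 the same function gives 5.0%.

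**Step 2: the 12–24 h interval.** For a pure exponential decline, linear area / true area = (x/2)(1 + e^−x)/(1 − e^−x), with x = 12 ln 2 / half-life.
- Placebo period, half-life 8 h: x = 1.040, factor 1.089.
- Omeprazole period: with ka 1 per h, a true AUC0-24 ratio of 1.25 needs clearance to fall by a factor of 1.441, so the half-life is 8 × 1.441 = 11.5 h, x = 0.722, factor 1.043.

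**Step 3: the whole profile.** At the protocol's sampling times, the linear rule overstates AUC0-24 by 2.40% with placebo and 1.38% with omeprazole. The measured ratio is 1.25 × 1.0138/1.0240 ≈ 1.2375. Applying the linear rule to the 12–24 h gap alone gives 1.2373, so that gap accounts for almost all of the shift.

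**Step 4: effect on the test.** ln(1.2375/1.25) = −0.0101, and 0.0101/0.0294 = 0.34 SE. The chance of concluding no interaction becomes 9.3% instead of 5.0%.

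**Step 5: range over half-life** (true AUC0-24 ratio 1.25, CV 7.8%, n = 14).

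| Half-life (h) | Measured ratio, ka 0.5 / 1.0 | Chance of concluding no interaction, ka 0.5 / 1.0 |
|---|---|---|
| 4 | 1.2391 / 1.2440 | 8.6% / 6.8% |
| 6 | 1.2345 / 1.2378 | 10.7% / 9.2% |
| 8 | 1.2353 / 1.2375 | 10.3% / 9.3% |
| 12 | 1.2387 / 1.2399 | 8.8% / 8.3% |
| 16 | 1.2415 / 1.2422 | 7.7% / 7.4% |
| 20 | 1.2435 / 1.2440 | 7.0% / 6.8% |

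With ka widened to 0.4–1.2 per h, the measured ratio is 1.2333–1.2448. Since 1.2333/1.25 = 0.987 and 1.2448/1.25 = 0.996, the shift is 0.4 to 1.3%. The error is 6.5–11.2%.

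**Step 6: dependence on the CV.** Over the same range of half-life and ka, the error is 5.8–7.8% at a CV of 15% and 5.6–7.0% at 20%.

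**Step 7: linear-up/log-down rule, same samples.** The true 1.25 is measured as 1.2503–1.2513, and the error at CV 7.8% is 4.7–4.9%.

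**The case against.** The bias in the ratio is only about 1%, and it changes the conclusion only in a narrow band near the limit. At a true ratio of 1.30 the chance of concluding no interaction is 0.3–0.7% with the linear rule against 0.2% without the bias, so a clearly larger change in AUC0-24 would not be missed. At 1.15 the shift only raises power, from 84.7% to 86–90%. The CV that makes a 1% shift count comes from cited studies not available here. The rule is pre-specified and unambiguous, and the half-life, which comes from log-linear regression, is unaffected by it and would show slower elimination. The Project aims section calls the study an exploratory pilot.

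All of this stands as a limit on size. A reader might infer that the linear rule nearly doubles the false no-interaction rate in general. The documents do not support that: it needs a true ratio at the margin, a CV near 7.8% and a half-life of roughly 6–10 h, and the documents give no half-life.

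The other strong point is that stopping at 24 h matters more. If AUC0-infinity truly rises by 25%, then for half-lives of 6–16 h the exact AUC0-24 ratio is only 1.09–1.18. The chance of concluding no interaction is then already 54–99.8%, and the linear rule multiplies it by only 1.00–1.18. That is a separate question about the choice of outcome. It does not justify leaving an avoidable bias in the outcome that was chosen, and the plan does apply an equivalence criterion to it despite the pilot label.

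**Conclusion.** The concern holds in a limited form. The rule and the sampling gap are facts of the plan. The direction of the bias, toward no interaction, follows whenever omeprazole slows gliclazide clearance. The error at the 1.25 limit exceeded 5% in every clearance scenario examined, but how far above 5% depends on a half-life and absorption rate that are assumed, and on whether the CV is as low as planned. The planned precision is what gives the shift its weight: on the log scale it is about 0.14 to 0.46 of the planned SE (0.0042/0.0294 to 0.0134/0.0294). It would not hide a large change in AUC0-24. It is a small, one-directional and avoidable error in the primary outcome, and the case for correcting it rests largely on how little the correction costs.

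**What to change.** In the Pharmacokinetic analysis section, state that gliclazide AUC0-t is computed by the linear-up/log-down trapezoidal rule: linear while concentrations rise, logarithmic while they fall. Apply the same to the AUC0-t part of AUC0-infinity, and hence to CL/F. Keep the linear rule for gliclazide as a sensitivity analysis, and for glucose and insulin as planned. Make the change before any concentrations are seen.

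The cost is one sentence and a different calculation option, with no added samples, subjects or visits. The change does not deal with truncation at 24 h, which should be considered separately.

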Gastrointestinal problems, such as gastroesophageal reflux disease (GERD) are common in T2D.¹⁴ A recent meta-analysis involving 9,067 cases and 81,968 controls showed a significant association between diabetes and the risk of GERD.¹⁵ The prevalence of GERD symptoms in patients with T2D could be as high as 40%.¹⁴ Therefore, millions of individuals are managing blood glucose and GERD concomitantly.¹⁶ Proton pump inhibitors (PPIs) are the medications of choice for GERD, and are primarily metabolised by CYP2C19.¹⁷ The potential for drug-drug interactions is highest for omeprazole and its stereo-isomer esomeprazole, which are metabolised almost entirely by CYP2C19.^{17,18} Furthermore, it has been shown that impact of PPIs on the PK, PD, and therapeutic response to drugs metabolised by CYP2C19 could depend on *CYP2C19* genotype, with highest effect seen in CYP2C19 normal metabolisers (extensive metabolisers, EM)^{19,20} and ultrarapid metabolisers (UM).²¹

Project aims

Considering the high prevalence of use of PPIs,²² the greater incidence of GERD in T2D and likely high concomitant use of PPIs with gliclazide, and the possibility of their interaction via CYP2C19, the primary aim of this pilot clinical study is to explore potential drug-drug interaction between gliclazide and omeprazole in CYP2C19 EM/UM metabolisers. The specific aims are:

1. To explore whether gliclazide PK is altered upon co-administration with omeprazole in healthy volunteers, CYP2C19 EM/UM metabolisers
2. To explore whether gliclazide PD is altered upon co-administration with omeprazole in healthy volunteers, CYP2C19 EM/UM metabolisers

Preliminary data

To our knowledge, there have been no studies exploring potential interaction between any PPI and gliclazide, in animals or humans. To explore this possible drug-drug interaction, we performed preliminary observational analyses in the large population-based GoDARTS study (UK). Briefly, our preliminary data suggest that co-treatment with PPIs, especially omeprazole, increases the risk of hypoglycaemia in patients with CYP2C19 EM/UM phenotype treated with gliclazide. This has been confirmed by better glycaemic response (lower HbA1c) associated with PPI use in EM/UM patients treated with gliclazide. These results support a biologically plausible hypothesis of possible interaction between PPIs and gliclazide, in relation to CYP2C19 genotype.

Study population

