Exclusion criteria for drug interaction study

- abnormalities in physical examination, ECG and routine clinical laboratory tests (including fasting blood glucose concentration)
- medication use during the 14 days prior and during the study periods
- grapefruit, grapefruit juice, alcohol, beverages or food containing methylxanthines use during 72 h prior and during the study periods

Participants will be randomised to specific treatment sequences using SAS Proc Plan procedure.

Drug interaction study design

A randomised, placebo controlled, two-sequence, two-period crossover study, with at least a 7-day washout period between the study periods will be conducted to compare the effects of gliclazide (40 mg, half of an 80 mg tablet of Diprian[®], Hemofarm d.o.o. Banja Luka, B&H, orally) and placebo with those of gliclazide combined with omeprazole (20 mg, Ulcosan[®], Bosnalijek d.d. Sarajevo, B&H, orally). Prior to administration of gliclazide, omeprazole or placebo will be administered once daily at 8 AM for 4 days (on day 1 until day 4) to assure PD steady-state. At 8 AM of the day 5, after an overnight fast (last meal at 9 pm of the previous day), the participants will be given a single dose of 40 mg gliclazide with 240 mL of water together with omeprazole or with placebo according to their treatment assignment.

The volunteers will be given both drugs (gliclazide + omeprazole or gliclazide + placebo) in a sitting position and they will not be permitted to lie down or sleep for the next 4 h after taking gliclazide. They will be under direct medical supervision throughout the 24 h following drug administration.

In order to counteract the blood glucose-lowering action of gliclazide, subjects will receive standardized meals: a breakfast at 30 min after gliclazide intake, snacks after 2 and 3 h, a lunch (warm meal) after 4 h, a snack after 6 h, a dinner after 8 h, and additional snacks at 10 h and 12 h after drug administration. The larger meals should be eaten within 10 minutes, and snacks within 5 minutes. No other food and drink (with the exception of water) or strenuous activities will be allowed.

[figure not shown]
Schematic design of the drug interaction study

- Period 1
 - Eight (8) subjects will receive treatment A on days D 1–5
 - Eight (8) subjects will receive treatment B on days D 1–5
- Wash-out period D6–14
- Period 2
 - Eight (8) subjects will receive treatment B on days D 15–19
 - Eight (8) subjects will receive treatment A on days D 15–19

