The costs of participants arising from their participation in the screening visit will be reimbursed in the amount of 50.00 BAM upon completion, and the costs of participants arising from their participation in the drug interaction study will be reimbursed in the amount of 400.00 BAM upon completion of the study. The funds will be paid to the participants' bank account.

Adverse events

Definitions

An *adverse event* (AE) is any untoward medical event affecting a clinical trial participant. Each initial AE will be considered for severity, causality or expectedness and may be reclassified as a serious event or reaction based on prevailing circumstances.

An *adverse reaction* (AR) is where it is suspected that an AE has been caused by a reaction to a trial drug.

A serious adverse event (SAE), serious adverse reaction (SAR) or suspected unexpected serious adverse reaction (SUSAR) is any AE, AR or UAR that at any dose:

- results in death or is life threatening
- requires hospitalisation or prolongation of existing hospitalisation
- results in persistent or significant disability or incapacity
- is a congenital anomaly or birth defect.

Recording and reporting adverse events and serious adverse events

The principal investigator should report any SAE that is both related to the research procedures and is unexpected, to the Ethics Committees which approved the study, and to the Faculty of Pharmacy University of Sarajevo, within 24 hours of the becoming aware of the event.

An adverse event log will be maintained in the CRF. The principal investigator on this study is medically qualified and will assess all adverse events for expectedness, seriousness and causality and will follow up to resolution or to within 30 days of the end of the study. The seriousness of the adverse event will be graded according to the *Common Terminology Criteria for Adverse Events (CTCAE) v5.0 Publish Date: November 27, 2017* (https://ctep.cancer.gov/protocoldevelopment/electronic_applications/docs/CTCAE_v5_Quick_Reference_5x7.pdf).

References

1. Feng, Y., *et al.* Ser1369Ala variant in sulfonylurea receptor gene ABCC8 is associated with antidiabetic efficacy of gliclazide in Chinese type 2 diabetic patients. *Diabetes Care* **31**, 1939-1944 (2008).
2. Standards of Medical Care in Diabetes-2017: Summary of Revisions. *Diabetes Care* **40**, S4-S5 (2017).

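### Insulin Cmin is read from a profile that includes the fasting pre-dose sample, so it may be insensitive to a rise in insulin; insulin Cmax would serve better, with AUC and Cavg kept as the main insulin measures

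*Combined protocol and SAP*

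**What the plan says.** All references are to the combined protocol and SAP.

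- *Project aims*, second specific aim: "To explore whether gliclazide PD is altered upon co-administration with omeprazole in healthy volunteers". The main outcome is a different one, gliclazide AUC0-t (*Power analysis*).
- *Pharmacodynamic parameters* lists five insulin measures: Cmin, Cavg over 0–4 h and 0–12 h, and AUC over the same two intervals. On the first it says: "The minimum glucose and insulin concentration will be determined by observation of the" profile. It gives no window and does not exclude the pre-dose value. No insulin peak is listed.
- *Blood sampling for glucose and insulin quantification*: "insulin: pre-dose (0 h), 0.5, 1, 1.5, 2, 2.5, 3" and onward to 12 h, which makes 16 samples.
- *Drug interaction study design*: gliclazide is given after an overnight fast, then "a breakfast at 30 min after gliclazide intake, snacks after 2 and 3 h", with further feedings at 4, 6, 8, 10 and 12 h.
- *Safety assessment and precaution measures* recognises a risk: "Since this combination of drugs can potentially induce risk of hypoglycaemia". On suggestive symptoms, "the blood glucose level will be measured using a glucometer and one of the standard measures of raising blood sugar will be applied".
- Neither *Pharmacodynamic parameters* nor *Statistical analysis* says what happens to glucose or insulin values drawn after such treatment.

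**The concern.** Gliclazide raises insulin, and omeprazole is suspected of strengthening gliclazide. A minimum taken over a profile that begins fasting and continues under repeated feeding tends to pick the part of the day where that effect is smallest. A pre-dose value cannot show an effect of that day's gliclazide at all, yet it is eligible to be the endpoint.

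The plan obtains Cavg by dividing AUC by the length of the interval, so the ratio of Cavg between treatments equals the ratio of AUC. The five insulin parameters therefore carry three distinct comparisons: AUC0-4, AUC0-12 and Cmin. If Cmin is insensitive, a ratio near 1 could be misread as evidence against a PD interaction.

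A separate and smaller matter is that glucose or glucagon given as rescue alters both analytes, and the plan does not say how later values enter the analysis.

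**Working it through.** **Plan's own figures.** The documents state no figure for insulin Cmin or for rescue. Their only related figure is the sample size for gliclazide AUC0-t. With a within-subject CV of 7.8%, limits of 80–125%, one-sided 5% per test and n = 14, equivalence power is 0.8505 at a ratio of 0.87 and 0.8468 at 1.15. This agrees with the stated 85%, and nothing below changes it.

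**Step 1: sampling against meals.** Taking the 0.5 h sample as drawn at the start of breakfast, the 0 h and 0.5 h samples are fasting. Time since last food for the other 14:

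- 0.5 h: samples at 1, 2.5, 3.5 and 4.5 h
- 1 h: samples at 1.5, 3, 4, 5 and 7 h
- 1.5 h: sample at 2 h
- 2 h: samples at 6, 8, 10 and 12 h

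**Step 2: assumed insulin profiles.** Fasting level is 1. The level d hours after food is 6 × (L/6)^(d/2), where L is the level at 2 h, set to 1, 1.5, 2 or 3 times fasting. Each sample has independent lognormal error with CV 10, 20 or 30%. A true rise multiplies insulin by 1.2 from 1 h on, and by either 1.0 or 1.2 at 0.5 h. The reading is exp(mean ln Y with the rise − mean ln Y without it).

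Two limits can be seen by hand. If L = 1, six samples tie at the fasting level (0, 0.5, 6, 8, 10 and 12 h), so without a rise the minimum is at 0 h in 1/6 = 17% of profiles and at 0 or 0.5 h in 2/6 = 33%. If L = 3, every later sample lies at 3 or above, so the minimum is practically always at 0 or 0.5 h. With no effect at 0.5 h, Cmin then reads a rise of 0%.

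Simulated range over all cells:

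| Quantity | Result |
|---|---|
| Minimum at 0 h, no rise | about 17–50% of profiles |
| Minimum at 0 or 0.5 h, no rise | 33–100% |
| Minimum at 0 h, with rise | 28–90% |
| Cmin reading of the 20% rise | 0–15% (7–15% if L = 1; 0–10% otherwise) |
| AUC0-4 and AUC0-12 reading | about 18–20% |
| Post-dose Cmin, no effect at 0.5 h | 0–14% |
| Post-dose Cmin, effect at 0.5 h | 20% |

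**Step 3: detection.** Assumptions: n = 14 (two sequences of 7, 12 df) and an added whole-profile within-subject CV of 15 or 25%. Share of trials with the lower 90% limit above 1 (5% is chance):

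| | No effect at 0.5 h | Effect at 0.5 h |
|---|---|---|
| Cmin, whole profile | about 5–30% | about 12–49% |
| Cmax | about 41–87% | about 42–87% |
| AUC0-12 | about 52–90% | about 53–91% |

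In these constant-rise cases Cmax never beat AUC0-12. In one time-varying pattern, a rise confined to samples after 4 h, Cmin (0–10%) can match Cmax (7–11%).

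**Step 4: rescue, for scale only.** Assume mean glucose of 5.5 mmol/L, so A = 5.5 × 4 = 22 or 5.5 × 12 = 66 mmol·h/L. Each rescue adds x = 2 to 6 mmol·h/L, and d more participants are rescued with omeprazole than with placebo. The ratio shifts by exp((d/n) × ln((A + x)/A)).

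- Largest, AUC0-4: (2/14) × ln(28/22) = 0.0345, or 3.5%. This needs all the added glucose to fall within 0–4 h.
- Largest, AUC0-12: (2/14) × ln(72/66) = 0.0124, or about 1.3%.
- Smallest, d = 1 and x = 2: 0.6% and 0.2%.
- With d = 0 the shift is zero.

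**The case against.** The strongest reply is that no conclusion changes. The aim is exploratory, no decision rule rests on insulin Cmin, and four planned insulin parameters read the rise almost in full. That stands and fixes the weight of the point. It does not justify keeping a measure that can be a pre-dose value when a better one is available from the same samples.

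Second, the insensitivity depends on assumed profiles. If insulin returns to fasting by 2 h after food, the minimum without a rise falls after dosing in 83% of profiles and Cmin recovers 7–15 of the 20 points. The model also gives snacks the same peak as meals. Halving the snack peaks, with no effect at 0.5 h, lifts Cmin detection in the L = 1.5 and 2 cells from about 5–8% to 11–20%. This stands: the documents support *may be insensitive*, not *is*. A reader might infer that Cmin will always be the pre-dose value; they do not show that.

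Third, omitting Cmax is not an error, and Cmax adds no power over AUC0-12 in the constant-rise cases. This stands too. Cmax is a better companion than Cmin, not a better main measure.

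On rescue, a reader might infer that the plan keeps all post-rescue values and that the PD results will be biased. The text is silent rather than stating such a rule. It gives no rescue rate or imbalance, and it schedules eight feedings to avoid hypoglycaemia. Counts may be largely recoverable, since "An adverse event log will be maintained in the CRF"; only the time of rescue is plainly unmentioned.

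**Conclusion.** The point holds as a minor one, confined to a secondary PD parameter under the second aim. The derivation rule lets a fasting value, including one drawn before gliclazide, serve as insulin Cmin. Under the assumed profiles a constant 20% rise reads as 0–15% in Cmin against about 18–20% in the AUCs. The direction follows from the sampling and meal times; the size rests on assumed post-meal insulin, sample error and presence or absence of an effect at 0.5 h, so both cases should be shown.

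A reader might go further and conclude that the PD aim fails or that the main result is compromised. The documents do not support that: insulin AUC and Cavg remain, and gliclazide AUC0-t and the sample size are untouched. The handling of post-rescue values is an optional clarification, not an error. Its effect is zero without rescue and at most about 3.5% on the glucose AUC0-4 ratio for an assumed excess of one or two participants.

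**What to change.** In *Pharmacodynamic parameters*:

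- Report insulin Cmax in place of insulin Cmin, and name insulin AUC and Cavg as the main insulin measures.
- If insulin Cmin is retained, take it from post-dose samples only, and note that this is a partial cure because the 0.5 h sample is still fasting.

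This costs SAP wording and no extra blood. The downside is that Cmax is a single-sample value under eight feedings, so it should support AUC and not replace it.

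Optional clarification:

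- State the main rule for glucose and insulin values after rescue, record rescue times and report rescues by treatment.
- Add a sensitivity analysis that omits post-rescue values, cut at the same time in both of that participant's periods. The cut depends on the outcome and shortens the interval for rescued participants, so it should stay a sensitivity analysis.
- Say that glucometer readings are safety data outside the PD profile, given that "Glucose concentrations will be measured at the laboratory of the General Hospital".

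This costs one CRF field for rescue time and a little analysis. With no rescues it changes nothing. No change to rescue treatment is proposed.
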